Sedestación en pelota	Báscula pélvica antero-posterior Rotación de tronco superior Báscula pélvica medio-lateral Rotación tronco inferior Flexión lateral del tronco Alcance anterior Alcance lateral derecho Alcance diagonal derecho Alcance lateral izquierdo Alcance diagonal izquierdo	  

Table 1: Stability exercises of the lumbopelvic region

In this simple blind randomized controlled pilot study, participants will be recruited from users of the rehabilitation center where the study will be carried out (Neurorehabilitation Clinic - Sant Cugat del Vallés). To carry out this study, there is already an agreement signed between the Neurorehabilitation Clinic and the International University of Catalonia.

The following participation criteria have been defined for this pilot study Inclusion criteria:

- Medical diagnosis of stroke with cortical or subcortical, ischemic or hemorrhagic involvement with more than 6 months of evolution
- Clinical symptoms of hemiplegia or hemiparesis
- Over 18 years of age
- Ability to understand and execute simple instructions
- Score equal to or less than 10 in the Spanish version of the Trunk Impairment Scale 2.0
- Be a frequent user of smartphone or tablet. Failing this, the direct family member / caregiver is considered.

Exclusion criteria:

- Appearance of any disease or aggravation of any of the comorbidities that the patient presents that prevents rehabilitation (example: dialysis)
- Suffer a second episode of Stroke.
- Fractures in any of the lower extremities or important structural alterations in the trunk.
- Death

30 participants will be recruited. No sample calculation will be performed as it is a convenience sample for a pilot study and it is a value very close to the total number of users with Strokes of the center where the study will be carried out. Another limiting factor of the sample is that the users will be monitored daily or weekly by an investigator assuming a ratio of 30 users / 1 therapist. In the recruitment process, patients will be informed about the study, they will be asked to sign an informed consent and the randomization between the experimental group and the control group will be done by computerized lottery and with the following interventions:

Experimental Group: Use of App for the daily performance (Monday to Friday) of lumbopelvic stability exercises (Table 1) apart from the usual physiotherapy treatment for 3 months.

Control Group: Regular physical therapy treatment.

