For statistical analysis, all subjects will be included, regardless of subsequent events such as protocol violations, lost data, or loss to follow-up. Qualitative and quantitative descriptive statistics will be used to characterize the sample depending on categorical (eg.: sex) or numerical (eg.: age) variables. In the analysis of results, the missing data will be imputed applying the imputation criterion of the last observation made. The distribution of the sample will be calculated according to the Shapiro-Wilk test and parametric and / or non-parametric tests will be used to calculate the significance of the results. The significance level (p) will be 0.05, that is, a confidence level of 95% and 5% of acceptable error. For the purpose of this study, it is proposed to analyze the difference between means and standard deviations of the variables both at the initial time and at 6 and 12 weeks. Its statistical significance will be calculated by the Student's t test or the Mann-Whitney U test for paired data. For the analysis of the effectiveness of the interventions, the evolution obtained in the different groups will be compared with the same statistical tests for independent samples. To assess the correlation between variables, the calculation of Pearson's coefficient and / or Spearman's coefficient will be used.

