## 7. Analysis of results:

According to the existing literature, performing muscle exercises for lumbopelvic stabilization leads to improvements in the balance in sitting, standing and gait in individuals with stroke. These results can be translated into the increase in participation in the ADL and the increase in the CV, factors to be taken into account in these individuals since their sequelae are usually highly limiting and chronic.

Usually, individuals who have suffered a stroke receive rehabilitation, by different disciplines where we find physiotherapy, according to their conditions and needs and with the common objective of achieving the maximum level of autonomy. Knowing that stroke patients can present chronic sequelae, their rehabilitation is perpetuated over time. It is thought that the use of an App can provide continuity to rehabilitation in its chronic phase, monitor and accompany the clinical evolution of the patient by the therapist. On the other hand, one can think that perhaps it is a method that allows reducing the resources, expenses in transfers and occupation of the rehabilitation center by chronic users.

The App will provide specific guidelines for carrying out lumbo-pelvic stabilization exercises and the possibility of viewing demonstration videos, with this it is intended to facilitate and encourage the performance of muscle exercises by the patient independently or with the help of a family member or caregiver. On the other hand, the patient will find a means that allows him to be in direct contact with the therapist in case of doubts about his rehabilitation process, as well as the therapist can contact the patient to monitor and follow up. In case of observing high levels of adherence to the use of the App as well as better results compared to conventional therapy, the use of the App as a new tool in neurorehabilitation can be considered. Even if chronicity leads us to think about maintaining physical condition, it is planned to find better results among individuals who will use the App as a therapeutic accompaniment for autonomous performance of muscle exercises for lumbopelvic stabilization adjacent to regular physical therapy.

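### Last observation carried forward is the only missing-data rule and has no sensitivity analysis, so the week-12 group difference can be biased, in a direction and by an amount the report could not show

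*Combined protocol and SAP*

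**What the plan says.** The statistical paragraph of section 6 (Material and methods) states that "all subjects will be included, regardless of subsequent events such as protocol violations, lost data, or loss to follow-up", and that "the missing data will be imputed applying the imputation criterion of the last observation made". It names no other missing-data method, no assumption about why data are missing and no sensitivity analysis, and neither does any other section.

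Outcomes are analysed "both at the initial time and at 6 and 12 weeks". For effectiveness, "the evolution obtained in the different groups will be compared with the same statistical tests for independent samples", that is, a t test or Mann-Whitney U test, at the 0.05 level. The App exercises are given "apart from the usual physiotherapy treatment for 3 months", so treatment runs up to the last visit.

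Section 7 (Analysis of results) says that "it is planned to find better results among individuals who will use the App as a therapeutic accompaniment". The same sentence opens with "Even if chronicity leads us to think about maintaining physical condition". It also ties possible use of the App to the outcome: "In case of observing high levels of adherence to the use of the App as well as better results compared to conventional therapy", the App can be considered as a new tool.

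**The concern.** With three visits, LOCF has a simple effect. A person lost before week 6 enters the week-12 comparison with a change of exactly zero. A person lost between weeks 6 and 12 enters with the week-6 change. If scores are still moving, these are not the week-12 values those people would have had. Including every participant does not cure this, because LOCF is the means by which the missing ones are included.

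At stake is the comparison on which section 7 partly rests its view of the App. With a single method and no second analysis, the report could not show whether the result was too small, too large or about right.

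**Working it through.** **No planned figure to reproduce.** The 30 participants are a convenience sample without a calculation, and the documents give no dropout rate, effect size, SD or time course.

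**Inputs from section 6:** 30 participants; visits at 0, 6 and 12 weeks; change compared between independent groups; level 0.05.

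**Assumed:** 15 per arm, two-sided test, SD 4, correlation 0.7 between visits, true week-12 difference 2.0 unless stated, loss at random. The complete-data standard error of the difference in change is then 4 × √(2 × 0.3) × √(2/15) ≈ 1.13.

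**Formula.** With a proportion *d* lost, the LOCF mean change in an arm is (1 − d) × week-12 change + d × (week-6 change if lost late, 0 if lost early).

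**A. App gains 1 then 2, control stable** (one reading of section 7)
- 20%/20% late: 0.8 × 2 + 0.2 × 1 − 0 = 1.8. Early: 0.8 × 2 = 1.6.
- 30% App/10% control late: 0.7 × 2 + 0.3 × 1 = 1.7. Early: 1.4.
- With *a* of 15 lost from the App arm: 2 − a/15 (late) or 2 − 2a/15 (early). No such pattern gives a value above 2.0.

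**B. App gains 2 then 4, control 1 then 2**
- 30%/10% late: (0.7 × 4 + 0.3 × 2) − (0.9 × 2 + 0.1 × 1) = 3.4 − 1.9 = 1.5. Early: 2.8 − 1.8 = 1.0.
- 10%/30% late: 3.8 − 1.7 = 2.1. Early: 3.6 − 1.4 = 2.2, so LOCF now favours the App.

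**C. Plateau: App gains 2 by week 6 and holds, control stable**
- Late loss: 2.0, no bias. Early loss at 20%/20%: 0.8 × 2 = 1.6.

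**D. What leavers do** (case A, 20% late loss). The true difference over everyone randomised is:
- 2.0 if leavers would go on gaining;
- 0.8 × 2 + 0.2 × 1 = 1.8 if they hold the week-6 level;
- 0.8 × 2 + 0 = 1.6 if they return to baseline.

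LOCF gives 1.8 each time: too small, right, and too large. A missing-at-random model gives 2.0 each time.

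**E. No true difference, both arms gain 2 then 4, loss 30% App/10% control**
- Late: 3.4 − 3.8 = −0.4. Early: 2.8 − 3.6 = −0.8. Swapping the loss rates reverses the sign.

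**Simulation** (20,000 trials per case, t test on change) reproduces these LOCF means and adds error rates.

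| Case | LOCF | Observed cases |
|---|---|---|
| A, 20%/20% late: power | about 33% | about 33% |
| B, 30%/10% late: power | about 24% | about 32% |
| B, 30%/10% early: power | about 12% | about 32% |
| E, 30%/10% late: type I error | about 6% | near 5% |
| E, 30%/10% early: type I error | about 11% | near 5% |

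With equal loss, or with no change in either arm, LOCF type I error stays near 5%. In case B with early 30%/10% loss its root mean squared error is about 1.50, against 1.28 for observed cases.

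**The case against.** **It is a small pilot, and losses may be few.** There is no named primary outcome, adherence is the first objective, and participants are monitored daily or weekly. One late loss per arm in case A moves the estimate by 1/15 ≈ 0.07, against a standard error of about 1.13. This limits the weight of the point. It does not remove it, because the plan still tests effectiveness at 0.05 and section 7 links consideration of the App to better results. That link is permissive and also requires high adherence; it is not a decision rule.

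**LOCF is not always wrong or less precise.** This stands. It is right for leavers who hold their week-6 level, late loss does no harm after a plateau, and in case A with equal loss its power matches that of observed cases. The plan gives no grounds for knowing that these conditions will hold.

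**The model has its own weakness.** It relies on data being missing at random and overstates the App gain if leavers lose it (case D). Hence the fix does not rest on the model alone.

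**A reader might infer that LOCF is simply conservative here, biased only against the App.** The documents do not support that. It needs a stable control arm, which rests on one loose clause in section 7, while controls receive active physiotherapy. Cases B and D show bias in favour of the App. **Nor can a reader infer that error control is safe, or that it is known to fail:** case E shows inflation, but only when both arms change and losses differ, and the documents do not say whether either will occur.

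**Conclusion.** The point holds. LOCF is the sole stated rule, nothing checks it, and it can bias the week-12 group difference. The bias is towards no effect if the App arm improves through week 12 and control is stable. It can go either way if both arms improve with unequal losses, or if leavers lose their gain.

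Under the assumed inputs, the shift on a true difference of 2.0 runs from none (late loss after a plateau) to about half (1.0, both arms improving, early 30%/10% loss), with a small overstatement (2.1 to 2.2) when the unequal loss is reversed. Type I error reaches about 6% to 11% only in the unequal-loss setting of case E. Confidence is high that the only rule is LOCF and that no second analysis is planned. The direction and size in this trial cannot be fixed from the documents.

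**What to change.** In the statistical paragraph of section 6:

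1. Make the main analysis a likelihood-based repeated-measures model on all observed baseline, 6- and 12-week data, with arm by visit, baseline adjustment and small-sample degrees of freedom such as Kenward-Roger. Use a rank-based or ordinal counterpart for the Rankin scale and other clearly non-normal scores.
2. Keep LOCF as a sensitivity analysis, beside one in which leavers stop gaining or return to baseline.
3. Report missingness by arm, visit and reason.

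If the main method is to stay, the minimum is one such alternative analysis beside LOCF.

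The cost is wording and programming, with no added visits or assessments. The downsides are reliance on missing at random, fitting a model in about 30 people, and a wider estimate. With baseline adjustment in both methods, case A at 20%/20% gave an SD of the estimate of 1.18 for the model against 1.06 for LOCF with late loss (about 11% larger), and 1.21 against 0.99 with early loss (about 22% larger). The small-sample correction matters: without it, a maximum-likelihood fit gave type I error of about 7% to 8% in 1,000 trials, and the corrected version was not tested here. The gain is less bias under random loss and a visible check, not more precision.

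As a separate point, the exclusion criteria in section 6 include events that can occur after enrolment, such as a second stroke or death, while the analysis paragraph keeps all subjects. These two passages must be reconciled, since LOCF would otherwise carry a pre-event score past the event.

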The information on the usual physiotherapy treatment will be collected together with the variables to be studied. At the end of the study, the description of the usual treatment, neuromotor development treatment, will be disclosed, which usually includes techniques for modulating the muscle tone of the affected body, postural control exercises, facilitation of functional movement and practice of tasks including walking.

To guarantee the blinding characteristic, the evaluations will be carried out by a third non-investigating person. The following variables will be studied through selected tests and questionnaires:

- Adherence to the use of the App by individuals from the EG: Data extracted by the administration panel of the App and System Usability Scale. Optimal use (100%) is considered 5 days / week, that is, a use from 0 to 20 days in 12 weeks months will be considered low adherence (0-33%), from 21 to 40 days (33-66%) regular adherence and 41 to 60 days (66-100% :) good adherence.
- QoL: EuroQol 5 dimensions 5 levels.
- Participation in AVD: Barthel Index.

- Functionality: Rankin scale.
- Sitting balance: Spanish versions of the Trunk Impairment Scale 2.0 and Function in Sitting Test.
- Standing balance: Spanish version of the Postural Assessment Scale for Stroke Patients, Berg Scale
- Record of the number of falls.
- Gait: stepping section of the Brunel Balance Assessment test and if they reach a score of 6 they will be evaluated with the G-Walk accelerometer (duration of double and individual support, cadence of the step, gait speed, stride length, length of step and elaborate steps).

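### Minor: the plan tests within-group change with a Mann-Whitney U test on paired data, but that test has no paired form and no paired rank test is named

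*Combined protocol and SAP*

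**What the plan says.** All of the relevant text is in the statistical paragraph of section 6, Material and methods.

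- **Comparison over time.** The plan will "analyze the difference between means and standard deviations of the variables both at the initial time and at 6 and 12 weeks". These are repeated measurements on the same participants.
- **Test for that comparison.** "Its statistical significance will be calculated by the Student's t test or the Mann-Whitney U test for paired data". The phrase at issue is "the Mann-Whitney U test for paired data".
- **Effectiveness.** In the sentence that follows, "the evolution obtained in the different groups will be compared with the same statistical tests for independent samples".
- **Choice between parametric and rank test.** "The distribution of the sample will be calculated according to the Shapiro-Wilk test and parametric and / or non-parametric tests will be used". The plan does not say whether the normality check is applied to raw scores or to differences, and it gives no cut-off for switching.

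The only other methods named in that paragraph are descriptive statistics, carrying forward the last observation, and Pearson or Spearman correlation. No paired rank test appears anywhere in the documents.

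**The concern.** Student's t test has a paired and an independent form, so one name can serve both sentences. Mann-Whitney U has only the independent form. The plan therefore names one rank test for two different designs, and for within-group change it names a procedure that does not exist.

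An analyst must either guess which paired test was meant or select Mann-Whitney U in the software. The second course treats the two visits as separate groups of people and discards the link between each participant's scores. What is at stake is the validity of the within-group p-values for outcomes analysed by ranks. The point does not extend to the between-group comparison.

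**Working it through.** **Inputs from the documents.** 30 participants in two groups, with no allocation ratio stated; significance level 0.05; Shapiro-Wilk used to inform the choice of test. The plan gives no power, effect size or SD, so it has no figure to reproduce.

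**Assumptions, not in the documents.** 15 per group; two-sided test; 0.5 SD change; pre-post correlation ρ of 0.5, 0.7 or 0.8; normal latent scores; complete data; and a strict switch (rank test if Shapiro-Wilk p < 0.05, otherwise paired t test).

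**Step 1: direction of the error.** With n pairs and common variance σ², the mean change has variance 2σ²(1 − ρ)/n. A test that ignores pairing works as if it were 2σ²/n. Its statistic is therefore too small by a factor of about √(1 − ρ), which is 0.71, 0.55 and 0.45 at ρ = 0.5, 0.7 and 0.8. At ρ = 0.5 the effective critical value is 1.96/0.71, about 2.77, so the true two-sided error rate is near 0.006 rather than 0.05. With positive correlation the error is conservative.

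**Step 2: Mann-Whitney U used alone on continuous paired scores** (n = 15; 10,000 runs per setting).

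| ρ | Type I error, Mann-Whitney | Power, Mann-Whitney | Power, signed-rank |
|---|---|---|---|
| 0 | 0.043 | 0.24 | 0.24 |
| 0.5 | 0.006 | 0.18 | 0.42 |
| 0.7 | 0.001 | 0.14 | 0.62 |
| 0.8 | 0.001 | 0.12 | 0.80 |

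The error rate at ρ = 0.5 agrees with step 1.

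**Step 3: the whole rule, Shapiro-Wilk and then paired t or rank test** (n = 15; 5,000 runs per setting; Monte Carlo standard error at most 0.7 points). Scores were left continuous or cut into 11 or 5 levels at equally spaced points from −1.5 to 2.0 SD. Power is in per cent at ρ = 0.5/0.7/0.8.

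| Shapiro-Wilk applied to | Outcome | Data sets reaching the rank test | Rule with Mann-Whitney | Rule with signed-rank |
|---|---|---|---|---|
| Differences | continuous | about 5% | 42/62/78 | 44/64/81 |
| Differences | 11 levels | 9–21% | 40/54/63 | 42/61/78 |
| Differences | 5 levels | 65–95% | 22/17/13 | 35/47/59 |
| Raw scores, either visit | continuous | 9–10% | 41/60/76 | 43/64/81 |
| Raw scores, either visit | 11 levels | 15–16% | 39/54/68 | 42/61/77 |
| Raw scores, either visit | 5 levels | 91–93% | 19/18/17 | 35/47/59 |

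For 5 levels with the check on differences, the losses are 35 − 22 = 13, 47 − 17 = 30 and 59 − 13 = 46 points.

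**Step 4: sensitivity** (check on differences).

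- *Type I error* of the rule with Mann-Whitney at ρ = 0.5/0.7/0.8: continuous 4.9/4.4/4.8%, 11 levels 4.2/3.9/3.5%, 5 levels 1.6/0.6/0.1%. None exceeds 5%.
- *Lower correlation.* At ρ = 0 the loss is under 1 point everywhere. At ρ = 0.3 it is about 1 point for continuous and 11-level outcomes and 5 points for 5 levels.
- *Group size*, 5 levels (3,000 runs per setting): 12 per group gives 20/16/10% against 29/38/47%; 18 per group gives 23/17/15% against 44/56/67%.

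**The case against.** The strongest reply is that the intent is plain. The plan itself separates paired data from independent samples, so an analyst would have to disregard the word paired to go wrong. Effectiveness is judged between groups, where the named tests are valid. The trial is a pilot with a convenience sample and makes no claim about within-group power. All of this stands, and it is why the point is minor. It does not make the sentence correct. The intention to pair is clear but the test is not: that signed-rank was meant is an inference, and the sign test is another candidate.

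A second reply concerns the size. The strict Shapiro-Wilk switch is a reading of the plan, whose wording would also allow both kinds of test to be run. That is fair, and the choice matters. For continuous scores at ρ = 0.8, Mann-Whitney used alone has 12% power against 80% for signed-rank, whereas under the switch the contrast is 78% against 81%. The largest losses also need a coarse outcome. An instrument such as "EuroQol 5 dimensions 5 levels" would supply one if its items were analysed singly, but the plan does not say whether items or an index will be used. The Rankin scale, also listed, is another possible candidate. Finally, the simulations use complete data, whereas carrying observations forward would add zero differences and ties. These points limit how far the figures can be pressed. They leave the naming error untouched.

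**Conclusion.** The concern holds, as a minor point. The rule for within-group change is wrong as written, because it names a test that cannot be applied to paired data as such. The error reaches only within-group p-values of outcomes analysed by ranks, and only if the named procedure is followed literally.

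Under the assumed switch, with 15 per group, a 0.5 SD change and correlations of 0.5 to 0.8, the loss of power with the check on differences is 3 points or less for continuous outcomes, up to 15 points for 11 levels, and 13 to 46 points for 5 levels. Without the switch the loss is also large for continuous scores. When visits are positively correlated, the error can hide real change but does not manufacture benefit. The between-group comparison is not affected by it.

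**What to change.** Replace the two test sentences in section 6 with: *Within-group changes: paired t test or Wilcoxon signed-rank test. Between-group comparisons of change: independent-samples t test or Mann-Whitney U test.*

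The second half leaves the between-group method as it is. It is spelled out so that neither comparison depends on a reference to the same tests. The investigators should confirm that signed-rank is the paired test they intend. The cost is one sentence of text, with no change to data collection, visits or procedures.

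### The between-group comparison of 'evolution' is undefined and ignores baseline; defining it and adjusting for baseline would cost almost nothing and usually add precision

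*Combined protocol and SAP*

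**What the plan says.** The statistical paragraph of section 6 first plans within-group comparisons "of the variables both at the initial time and at 6 and 12 weeks". For effectiveness it then says only that "the evolution obtained in the different groups will be compared with the same statistical tests for independent samples". The tests in question are Student's t and Mann-Whitney U.

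Nothing in the document gives evolution a formula. It could be change to 6 weeks, change to 12 weeks, change between the two, or the score at follow-up. No covariate, ANCOVA, regression or mixed model is named, and no time point is marked as the main one.

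Other parts of section 6 bear on the point:
- Size: 30 participants, and "No sample calculation will be performed as it is a convenience sample for a pilot study".
- Allocation: "the randomization between the experimental group and the control group will be done by computerized lottery", with no ratio or stratification stated.
- Entry: "Score equal to or less than 10 in the Spanish version of the Trunk Impairment Scale 2.0". The same scale is also a sitting-balance outcome.
- Missing values: "the missing data will be imputed applying the imputation criterion of the last observation made".
- Outcomes that are not multi-level scores: "Functionality: Rankin scale", the Brunel stepping section and falls. Gait is measured conditionally: "if they reach a score of 6 they will be evaluated with the G-Walk accelerometer".

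**The concern.** This one sentence carries the second objective in section 4 and every hypothesis in section 5 except the first, on adherence. Section 7 makes considering the App as a new tool depend partly on the result. Two things are left open.

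First, the estimand. A change score and a follow-up score can differ greatly in precision. If the choice is made after the data are seen, the 5% error rate no longer holds.

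Second, efficiency. The sample is about as large as the centre can supply, so extra precision will not come from recruiting more patients. An unadjusted comparison leaves unused, or uses in a fixed and usually suboptimal way, a baseline measurement that each patient already provides.

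**Working it through.** The plan has no power or sample-size figure to reproduce.

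**Inputs.** From section 6: N = 30, significance level 0.05, assessments at baseline, 6 and 12 weeks. Assumptions, because the documents are silent: 15 per arm, normal scores, two-sided tests, r varied, and a true difference of 0.8 SD for power.

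**Change-score reading, equal SDs.** In units of the score variance, the change score has 2(1 − r). ANCOVA has (1 − r²) × (N − 3)/(N − 4), where 27/26 = 1.038 is the expected cost of estimating the slope. The ratio is (1 + r)/2 × 27/26.

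| r | ANCOVA/change variance | Power, change vs ANCOVA |
|---|---|---|
| 0.5 | 0.75 × 1.038 = 0.779 | 56% vs 67% |
| 0.7 | 0.85 × 1.038 = 0.883 | 78% vs 83% |
| 0.8 | 0.90 × 1.038 = 0.935 | 92% vs 93% |
| 0.9 | 0.95 × 1.038 = 0.987 | equal |
| 0.95 | 0.975 × 1.038 = 1.012 | not needed |

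Break-even is r = 2 × 26/27 − 1 = 0.926. Power comes from 40,000 simulated trials per setting. Type I error was about 5% for the change-score test, the follow-up test and ANCOVA alike.

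**Unequal SDs.** With s the follow-up SD divided by the baseline SD, the ratio is s²(1 − r²)(27/26)/(1 + s² − 2rs). For example, s = 1.2 and r = 0.7 give 1.44 × 0.51 × 1.038/0.76 = 1.003. Change scores are slightly better in these ranges:
- s = 1.1: r of about 0.79 to 0.96
- s = 1.2: r of about 0.69 to 0.91
- s = 1.3: r of about 0.62 to 0.87

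At s = 0.8 or 0.9 ANCOVA wins at every r. With a known slope ANCOVA is never worse than the change score, so the expected loss is bounded by 27/26, or 3.8%.

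**Follow-up reading.** The ratio is (1 − r²) × 27/26: 0.78 at r = 0.5, 0.53 at 0.7 and 0.20 at 0.9. Break-even is r = √(1/27) = 0.19, or about 0.20 allowing for the lost degree of freedom. Power at r = 0.7 is 56% vs 83%.

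**Leaving the reading open.** Under no effect, reporting whichever of the change or follow-up tests is significant gives a type I error of about 9% for r from 0.5 to 0.9.

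**Trunk Impairment Scale 2.0.** The entry cap shrinks the baseline variance to v, and the ratio becomes (1 − r²)(27/26)/[(1 − r)²v + 1 − r²]. If the cap fell at the population mean (an assumption), v = 0.363. The ratio is then 0.93, 0.98, 1.00 and 1.02 at r = 0.5, 0.7, 0.8 and 0.9, with r taken before restriction. Break-even is r = 0.81 before restriction, or 0.64 among those enrolled. For a scale correlated 0.8 with it (also assumed), the ratios at r = 0.7, 0.8 and 0.9 are 0.94, 0.97 and 1.01.

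**Last-observation imputation.** If a fraction p of 12-week values are baseline carried forward, r becomes (1 − p)r + p. At r = 0.7, p = 0.1 and 0.2 give 0.73 and 0.76, and ratios of 0.90 and 0.91.

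**Ordinal and rank branch (simulated).** For a five-level outcome with equal categories, Mann-Whitney on change vs rank ANCOVA has power 42% vs 58% (r = 0.5), 59% vs 71% (0.7) and 71% vs 81% (0.8). For a continuous score the comparison is 54% vs 63%, 76% vs 78% and 90% vs 89%, so there is no gain from about r = 0.75. A proportional-odds model with baseline is fragile here. With three occupied levels (15/70/15%), 9% to 46% of fits were unusable as r rose from 0.7 to 0.9, while only 1% to 9% were flagged as non-converged.

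**The case against.** The strongest reply is that nothing here is wrong. This is a convenience-sample pilot with no power target to miss, an unadjusted comparison of randomised groups is valid, and the first-listed objective, adherence, is untouched. All of that stands. A reader might infer that the planned test is biased or that the trial falls short of a promised power; the documents support neither.

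The second reply is that the gain is uncertain. A reader might take a correlation of about 0.9 as a general limit below which ANCOVA always wins. That holds only for the change-score reading with equal SDs, and the documents give no SDs. Uneven response to an exercise programme could widen the follow-up spread, and the entry cap reduces the gain for trunk and balance scales. In stable chronic patients r may also be high, and carrying values forward raises it further. This narrows the expected benefit but does not reverse the advice, because the loss stays within 3.8%.

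Third, one linear model does not fit every outcome. This also stands. Falls are a count with no described baseline, G-Walk data exist only for those who pass the gait threshold, and the Rankin scale has few levels. A reader might reach for proportional odds there, but at this size separation often goes unflagged, so a fallback triggered by non-convergence would often not operate.

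Stratified allocation could also help precision. It would change the randomisation, whereas baseline adjustment changes only the analysis.

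**Conclusion.** The point holds as a recommended improvement in pre-specification and precision. Defining evolution is worthwhile at any r, because the error rate is guaranteed only for a reading fixed in advance. Baseline adjustment cuts the variance relative to change scores by about 22% at r = 0.5, 12% at 0.7, 6.5% at 0.8 and 1% at 0.9, given 15 per arm, normal scores and equal SDs. It cuts it by much more if evolution means the follow-up score. If the SD rises at follow-up, the advantage ends at a lower r; if it falls by 10 to 20%, ANCOVA always wins. For the Trunk Impairment Scale 2.0 little or no gain over change scores should be expected, and a reduced gain for scales that track it.

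The arithmetic is firm. The benefit this trial would actually see is unknown, because the documents give neither r nor the SDs.

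**What to change.** Define evolution, and replace the between-group sentence in section 6 with:

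> For each multi-level scale score, and each G-Walk measure with a baseline value, the groups will be compared at 12 weeks, and likewise at 6 weeks, by ANCOVA of the score on arm and that outcome's baseline, reporting the adjusted difference with its 95% CI. If the residuals are clearly non-normal, a rank ANCOVA on the baseline score will be reported as a check. The Rankin scale and the Brunel stepping section will be compared by rank ANCOVA with baseline, with category counts by arm.

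Proportional odds should not be the main analysis for those last two outcomes. Falls should be left out of the ANCOVA. App adherence and the System Usability Scale concern the experimental group only and do not change.

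The cost is wording, one degree of freedom, and at most about 4% in variance against change scores. No extra data or visits are needed.
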